¹¹ Samples for correlative research are to be collected as indicated in Section 5

Version Date: 09/14/2021

3.10 Criteria for Removal from Protocol Therapy and Off Study Criteria

Prior to removal from study, effort must be made to have all patients complete a safety visit approximately 30 days following the last dose of study therapy. The reason for removal from protocol therapy and off study will be clearly documented in the medical record. Additional safety visits and follow-up will continue as per Section 3.8.

3.10.1 Criteria for Removal from Protocol Therapy

- Completed planned treatment regimen/duration (i.e., up to 6 cycles)
- Confirmed hematologic or radiographic disease progression
- Unacceptable toxicity occurring at any time during treatment as listed in Section 3.2 or those toxicities listed in Section 3.5 that require treatment to be stopped.
- Intercurrent illness that prevents further administration of treatment
- Requirement for use of prohibited therapies as listed in Section 4.2
- Pregnancy
- Subject's requests to be withdrawn from protocol therapy
- Noncompliance with trial treatment or procedure requirements that requires removal in the opinion of the PI
- Investigator's decision to withdraw the subject
- Study is cancelled for any reason

3.10.2 Off-Study Criteria

- Subject requests to be withdrawn from study
- Subject is lost to follow-up
- Death
- Study is cancelled for any reason

3.11 COST AND COMPENSATION

3.11.1 Costs

NIH does not bill health insurance companies or participants for any research or related clinical care that participants receive at the NIH Clinical Center. If some tests and procedures performed outside the NIH Clinical Center, participants may have to pay for these costs if they are not covered by insurance company. Medicines that are not part of the study treatment will not be provided or paid for by the NIH Clinical Center.

3.11.2 Compensation

Participants will not be compensated on this study.

3.11.3 Reimbursement

The NCI will cover the costs of some expenses associated with protocol participation. Some of these costs may be paid directly by the NIH and some may be reimbursed to the participant/guardian as appropriate. The amount and form of these payments are determined by the NCI Travel and Lodging Reimbursement Policy.

Version Date: 09/14/2021

4 CONCOMITANT MEDICATIONS/MEASURES

Medications or vaccinations specifically prohibited in the exclusion criteria are not allowed during the ongoing trial. If there is a clinical indication for one of these or other medications or vaccinations specifically prohibited during the trial, discontinuation from trial therapy or vaccination may be required.

4.1 ACCEPTABLE MEDICATIONS

All treatments that the investigator considers necessary for a subject's welfare may be administered at the discretion of the investigator in keeping with the community standards of medical care. All concomitant medication will be recorded on the case report form (CRF) including all prescription, over-the-counter (OTC), herbal supplements, and IV medications and fluids. If changes occur during the trial period, documentation of drug dosage, frequency, route, and date may also be included on the CRF.

All concomitant medications received within 28 days before the first dose of trial treatment and 30 days after the last dose of trial treatment should be recorded.

4.2 PROHIBITED MEDICATIONS

Patients are prohibited from receiving the following therapies during treatment on this trial:

- Other therapy for the disease under study not specified in this protocol, unless specifically noted as permitted
- Investigational agents other than rhIL-15 and obinutuzumab
- Radiation therapy

NOTE: Radiation therapy to a symptomatic solitary lesion may be allowed at the investigator's discretion.

• Live vaccines within 30 days prior to the first dose of trial treatment and while participating in the trial. Examples of live vaccines include, but are not limited to, the following: measles, mumps, rubella, varicella/zoster, yellow fever, rabies, BCG, and typhoid vaccine.

Patients who, in the assessment by the investigator, require the use of any of the aforementioned treatments for clinical management should be removed from study treatment. Patients may receive other medications that the investigator deems to be medically necessary.

Version Date: 09/14/2021

5 CORRELATIVE STUDIES FOR RESEARCH

5.1 BIOSPECIMEN COLLECTION

This study will attempt to use rhIL-15 to increase NK cell number and activity, thereby enhancing the ADCC of obinutuzumab in treatment of patients with relapsed and refractory CLL. ADCC capacity of *ex vivo* PBMCs will be tested on CD20-expressing cell lines before, during and after protocol treatment. Differences in immune cell subsets associated with administration will be followed throughout treatment to both study the effects of combined rhIL-15/obinutuzumab therapy on the immune system, and to identify potential biomarkers that would be predictive of response.

			Time Points							Supervising
Sample	Collection Details*	Baseline	C1 D4	C1 D5	C1 D8	C1 D11		C2-6 D8	Follow up#	Laboratory/ Investigator
Blood Samples										
Lymphocyte subset testing	• 2 x 10mL K ₂ EDTA tubes (lavender top)	X	(X)		X	(X)	(X)	(X)	(X) ¹	Immunology section, NIH CC
ADCC of obinutuzumab	• 3 x 10mL NaHep tubes (green top)	(X) ²	(X) ²	(X) ²	(X) ²			(X) ²		[name]
Tissue immune cell subsets (comparison)	• 1 x 5mL green-top tube	(X)			(X)				(X)	[name]
Circulating tumor DNA, plasma banking	• 1 x 10mL K ₂ EDTA tube • 1 x 10mL Streck/BCT tube	X	(X)		(X)			(X)	X ³	[name] (Leidos CSL)
Anti-IL-15 antibodies	• 1 x 4mL SST tube	X					X		X^1	
Tissue Samples										
Tissue immune cell subsets	 Two core biopsy samples in RPMI 1640 with 10% human serum and antibiotics One core biopsy sample in formalin NOTE: Samples may be tumor tissue or bone marrow aspirate/biopsy 	(X)			(X)				(X)	[name]/ (RPMI 1640) and DLM/ NCI LP (formalin)
Other Samples										
Germline DNA	• Blood, Buccal Swab, or Saliva (preferred)	X								[name]

Version Date: 09/14/2021

		Time Points						Supervising		
Sample	Collection Details*	Baseline	C1 D4	C1 D5		C1 D11		C2-6 D8	Follow up#	Laboratory/ Investigator

⁽X) = Optional; samples will be collected if adequate time/staff available for processing. If an optional sample is not collected at baseline, it would also not be collected in follow-up unless specifically requested by the PI.

5.2 SAMPLE COLLECTION AND PROCESSING

5.2.1 Summary

The planned analyses described below may be done on leftover and/or shared sample portions from the respective laboratories, as needed. In addition to the prospectively collected samples below, leftover portions of samples sent for routine laboratory testing (e.g., plasma from CBC/hematologies) may also be retrieved for research tests prior to being discarded. The planned prospective analyses are identified below; laboratories may share resources or collaborate on analyses, if appropriate.

Portions of all samples may be banked for future research analyses; prospective consent will be obtained during the informed consent process.

The blood drawing limits for research purposes are as follows:

• For adult subjects: The amount of blood that may be drawn from adult patients for research purposes shall not exceed 10.5 mL/kg or 550 mL, whichever is smaller, over any eightweek period.

All samples will be delivered to the laboratory of [name], Lymphoid Malignancies Branch. The laboratory staff will handle processing or delivery/shipping of associated labs, if applicable. To arrange for sample processing, contact: [name], Lymphoid Malignancies Branch ([name]; [contact]), [name], Lymphoid Malignancies Branch ([name]; [contact]) or [name]., Lymphoid Malignancies Branch ([name]; [contact]). Tissue samples will also be sent to the Hematopathology Section of Laboratory of Pathology, NIH Clinical Center, by courier service.

5.2.2 Blood Samples

All blood samples will be drawn by NIH Clinical Center phlebotomy, outpatient clinic, or day hospital staff.

5.2.2.1 Lymphocyte subset testing by flow cytometry (FACS)

• Collect blood in EDTA tubes; gently invert tubes 8-10 times immediately after collection.

^{*}Tubes/media may be adjusted at the time of collection based upon materials available or to ensure the best samples are collected for planned analyses.

^{*}Subjects who discontinue treatment for a reason other than disease progression and who do not start new treatment should continue to have study bloods collected at the scheduled time points.

¹ At the end of treatment only.

² For ADCC of obinutuzumab, Baseline, C1D4, C1D5 and C1D8 samples should be collected for at least one patient per dose level, and for at least three patients at the MTD; C2-6 samples may be collected at the discretion of the PI, but are not required.

³ At each follow-up visit prior to disease progression, as specified in Section 3.8.2.

Version Date: 09/14/2021

• Labels listing the patient's name, date of birth, date and time of the blood draw will be affixed to all the tubes by the staff person who obtained the samples.

• Lymphoid Malignancies Branch Clinical Research personnel will arrange for these samples to be delivered to: Immunology Lab, NIH Clinical Center [name]. If the Immunology Section Laboratory is unable to perform this analysis on the specified days, this assessment maybe omitted or replaced with standard TBNK panel.

5.2.2.2 Antibody-dependent cell cytotoxicity (ADCC) of obinutuzumab

- Collect blood in sodium heparin tubes; gently invert tubes 8-10 times immediately after collection.
- Samples will be processed per established laboratory techniques.

5.2.2.3 Cell-free DNA (cfDNA)/circulating tumor DNA (ctDNA) and plasma banking

- Collect blood in EDTA and cell-free DNA (i.e., Streck BCT) tubes; gently invert tubes 8-10 times immediately after collection.
- Lymphoid Malignancies Branch Research personnel will arrange for these samples to be delivered to Clinical Support Laboratory, Leidos Biomedical Research, Inc.in Frederick, MD, for sample processing per established techniques.

5.2.2.4 Anti-IL-15 antibody testing

- Collect blood in a 4mL SST tube; gently invert tubes 8-10 times immediately after collection.
- Lymphoid Malignancies Branch Research personnel will arrange for these samples to be delivered to Clinical Support Laboratory, Leidos Biomedical Research, Inc.in Frederick, MD, for storage and further analysis.
- Samples will be batch processed and analyzed per the procedure outlined in Appendix B after the last patient has been enrolled and completed treatment, or sooner if there is clinical suspicion for anti-IL-15 antibody formation.

5.2.3 Tissue Samples

Potential site(s) of biopsy include, but are not limited to: bone marrow, extramedullary disease/masses, and lymph nodes. The type of procedure to be done and manner in which it will proceed (e.g., excision/core, single vs. multiple sites of biopsy) will be discussed with the patient prior to the biopsy procedure.

The patient will be reminded that all sampling for research is voluntary. In the case of lymph node excision or core needle biopsy, these will be performed per routine standard of care by Surgery Consultants or Interventional Radiology, as appropriate; and, a procedure-specific consent form will be signed by the patient prior to the procedure. Conscious sedation may be used, if warranted, and the use and risks are acceptable to the patient. Skin biopsies may be performed by qualified clinical staff. The use of image-guidance other than ultrasound for collection of research samples is not expected (i.e., radiation exposure for research purposes is not expected).

Core tumor tissue (or bone marrow aspirate/biopsy) samples will be collected and placed in appropriate media (e.g., RPMI 1640 with 10% human serum and antibiotics, and formalin) and processed per established techniques. As indicated (Sections **5.1** and **5.2**), samples will be sent to the Department of Laboratory Medicine (DLM)/ NCI Laboratory of Pathology (LP) for concurrent routine analysis and reporting in addition to research testing (i.e., [name] Lab).

Version Date: 09/14/2021

5.2.4 Other Samples

5.2.4.1 Germline DNA

Germline DNA will be collected by blood, buccal swab, and/or saliva samples (preferred). These will ideally be collected at baseline; however, may be collected at any point on study based on supplies. Standardized, commercial collection kits or tubes will be used (e.g., 1, 5-10 mL K₂EDTA tube for blood; Isohelix SK-1 for buccal swabs; Salviette/Oragene® for saliva). In the case of buccal swabs, two (2) samples may be collected in order to ensure adequate DNA collection.

The samples will be processed and DNA extracted/isolated per kit instructions and established techniques.

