1.2.2 Diagnosis and Staging of CLL

According to the 2008 International Workshop on Chronic Lymphocytic Leukemia (IWCLL)(9), updated in 2018(10), diagnosis of CLL requires meeting two criteria:

- presence of at least 5x10⁹ /L morphologically mature-appearing small lymphocytes in the peripheral blood (PB), and
- circulating monoclonal B lymphocytes defined by PB flow cytometry; the characteristic pattern of CLL immunophenotype is: expression of the T-cell surface antigen (CD5), expression of B-cell surface (CD19, CD20, and CD23), and low-level expression of surface Ig with either κ or λ (but not both) light chains.

Two staging systems are widely used: the Rai system(11), and the Binet system(12), both of which are simple and inexpensive owing to their reliance solely on a physical exam and standard laboratory tests (Table 1).

Table 1: Rai Staging System

Stage	Risk	Manifestation	Median survival (months)
0	Low	Lymphocytosis	120
I	T.,4., 1!4.	Lymphocytosis with adenopathy	108
II	Intermediate	Lymphocytosis with hepato/splenomegaly	94

Version Date: 09/14/2021

Stage	Risk	Manifestation	Median survival (months)
III	IIi ah	Lymphocytosis with anemia (Hemoglobin <11 g/dL)	60
IV	High	Lymphocytosis with thrombocytopenia (platelets <100,000 / μL)	60

As Rai staging cannot identify patients with aggressive clinical phenotypes who are at risk for treatment-refractory disease or early relapse, many prognostic and predictive marks have been developed, including IGHV mutation status(5), ZAP-70(7), and β2microglobulin(13).

Newly diagnosed patients with asymptomatic early stage disease (Rai 0, Binet A) should be monitored without intervention unless there is an evidence of rapid disease progression. Symptomatic patients with advanced stage (Rai 3 or 4, Binet B or C) stages usually benefit from treatment. 2008 IWCLL defines active disease by following criteria(9):

- Evidence of progressive marrow failure as manifested by the development of, or worsening of, anemia and/or thrombocytopenia
- Massive (i.e., at least 6 cm below the left costal margin) or progressive or symptomatic splenomegaly
- Massive (i.e., at least 10 cm in longest diameter) or progressive or symptomatic lymphadenopathy

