2.1.2 Exclusion Criteria

- 2.1.2.1 Current or prior anti-cancer treatment prior to the first dose of rhIL-15 as defined below:
 - Chemotherapy, targeted small molecule therapy, or other anti-cancer treatment not otherwise specified below within 2 weeks
 - Radiation therapy within 2 weeks
 - Anti-cancer monoclonal antibody (mAb) treatment within 4 weeks
 - Use of an investigational agent (e.g., biologic, drug, or other) within 4 weeks
 - Allogeneic stem cell transplant within 100 days
 - Systemic treatment for graft versus host disease (GVHD), including but not limited to oral or parenteral corticosteroids, ibrutinib, and extracorporeal phototherapy, within the last 12 weeks
- 2.1.2.2 Persisting toxicity related to prior therapy (including GVHD) of grade > 1, with the exception of the following: alopecia or sensory neuropathy grade ≤ 2 , or other grade ≤ 2 not constituting a safety risk based on investigator's judgment

Version Date: 09/14/2021

2.1.2.3 Current use of immunosuppressive medication, EXCEPT for the following:

- Intranasal, inhaled, topical steroids, or local steroid injection (e.g., intra-articular injection);
- Systemic corticosteroids at physiologic doses ≤ 10 mg/day of prednisone or equivalent; or,
- Steroids as premedication for hypersensitivity reactions (e.g., CT scan premedication)
- 2.1.2.4 Presence of Richter's transformation.
- 2.1.2.5 Patients requiring immediate cytoreduction, if they had no prior treatment with a drug that has an established clinical benefit.
- 2.1.2.6 Presence of uncontrolled intercurrent illnesses including but not limited to ongoing or active infection, symptomatic congestive heart failure, unstable angina pectoris, cardiac arrhythmia, cognitive impairment, active substance abuse, or psychiatric illness/social situations that in the view of the Investigator would preclude safe treatment and limit compliance with study requirements
- 2.1.2.7 Presence of active bacterial infections, documented HIV infection, PCR evidence for active or chronic hepatitis B or hepatitis C, or positive screening HBV/HCV serology without documentation of successful curative treatment (see Section 3.5.2.1 for data on obinutuzumab administration in patients with HBV, and Section 12.5 for IL-15 administration in HIV-positive patients)

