2.4.5 Research Correlates

NOTE: See Section 5 for additional information. The following sample types will be collected for correlative research studies:

[figure not shown]
- Required:
 - o Blood samples for lymphocyte subset testing and circulating tumor DNA
 - o Blood, buccal swab, or saliva for germline DNA
- Optional:
 - o Blood samples for ADCC of obinutuzumab, tissue immune cell subset comparison
 - o Bone marrow biopsy
 - o Tumor biopsy

Version Date: 09/14/2021

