5.3.3 ADCC Analysis

Peripheral blood mononuclear cells (PBMCs) should be isolated by Ficoll-Hypaque Density Gradient Centrifugation. The viable cells should be viably frozen and stored in liquid nitrogen. The ADCC assay will be performed on the same occasion for all samples of a given patient. Vials of frozen cells will be thawed using standard procedures 18 hours before the assay in accord with our experience with normal donors. 1.5 million of patient's PBMCs obtained before and on day 15 following IL-15 injection will be tested in aliquots as follows:

- Tested alone
- Tested with untreated Raji cells and with Raji cells coated with an antibody to CD20 for 5 hours
- In addition, we may utilize an ATL cell line in addition to Raji cells. These cell populations will be stained with CD107, CD3, CD56, and CD94.

5.3.4 cfDNA/ctDNA

Since the methods of molecular monitoring in the peripheral blood is an emerging field with numerous technologies under development, the storage of peripheral blood mononuclear cells (PBMC), serum, and plasma will all be performed allowing for future comparison of the different

Version Date: 09/14/2021

compartments for analytes that include cell-free circulating tumor DNA (ctDNA), and RNA sequencing of circulating tumor cells. Studies to be performed on these samples include: cfDNA/ctDNA for liquid genotyping as a non-invasive dynamic monitoring of disease as well as monitoring for individual molecular aberrations that herald progression or disease transformation; specifically, amplification and sequencing of the VDJ segment of the immunoglobulin receptor is planned. Germline DNA obtained from saliva, blood, or buccal mucosa will be used to discriminate somatic from germline mutations during cfDNA and ctDNA analyses.

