5.3.5 DNA/RNA Sequencing

Genomic DNA and total RNA will be extracted from tumor samples using a Qiagen All-prep kit. For individual target genes that are recurrently mutated in CLL, classical Sanger sequencing will be performed on PCR amplicons, using primers surrounding the known sites of mutation. To broadly assess mutations, next generation sequencing (e.g., on an Illumina HiSeq 2000 platform) will be employed, using a paired end sequencing strategy of libraries constructed from tumor DNA. DNA will either be sequenced in its entirety from a whole genome library or will be first enriched for exonic sequences using the Agilent Sure Select system, aiming for 30X or 100X average coverage per base, respectively. The sequence fragments will be mapped back to the genome using the BWA algorithm. Of sequences overlapping a particular base pair in the genome, the percent mutant calls greater that 20% with a minimum of 25X coverage will be considered as an arbitrary threshold for single nucleotide variants (SNVs). SNVs that are not present in the matched normal sample will be considered candidate somatic mutations.

A related technology, RNA-Seq, utilizes RNA from the tumor specimen to create a cDNA library for high-throughput sequencing. RNA-seq will be performed using Illumina kits followed by high-throughput sequencing on an Illumina HighSeq 2000 machine. The cutoffs for coverage and percent mutant calls mentioned above will also be used to identify putative SNVs. RNA sequencing will also be used to read out digital gene expression across the genome as described.

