5.5.4 Genetic Counseling

Subjects will be contacted with a request to provide a blood sample to be sent to a CLIA certified laboratory. If the research findings are verified in the CLIA certified lab, the subject will be offered the opportunity to come to NIH to have genetic education and counseling to explain this result; at the time of any such event(s), these activities will be funded by the NCI/CCR in consideration of the specific circumstances. If the subject does not want to come to NIH, a referral to a local genetic healthcare provider will be provided (at their expense).

This is the only time during the course of the study that incidental findings will be returned. No interrogations regarding clinically actionable findings will be made after the primary analysis.

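### Unsorted blood is allowed as the germline comparator in CLL; where it is used and leukemic cells are numerous, the somatic filter is likely to drop clonal mutations

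*Combined protocol and SAP*

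**What the plan says.** Germline DNA is a required baseline sample, and three sources are accepted. Section 2.4.5 lists "Blood, buccal swab, or saliva for germline DNA". The table in Section 5.1 gives the same three, and Section 5.2.4.1 repeats them: "Germline DNA will be collected by blood, buccal swab, and/or saliva samples (preferred". Saliva is therefore preferred, but blood is allowed for any patient. Collection is ideally at baseline but may happen at any time on study. On processing, the section says only: "The samples will be processed and DNA extracted/isolated per kit instructions and established techniques".

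The sample has two uses:

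- Section 5.3.4, liquid genotyping: "Germline DNA obtained from saliva, blood, or buccal mucosa will be used to discriminate somatic from germline mutations during cfDNA and ctDNA analyses".
- Section 5.3.5, tumor sequencing: "SNVs that are not present in the matched normal sample will be considered candidate somatic mutations". The same paragraph sets a threshold for calling a variant (more than 20% mutant reads, at least 25X coverage) and target depths of 30X (genome) and 100X (exome). It does not say how many mutant reads make a variant present in the normal.

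Three other places bear on the point:

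- Section 1.2.2 makes circulating cells part of the diagnosis: "presence of at least 5x10⁹ /L morphologically mature-appearing small lymphocytes in the peripheral blood (PB".
- Section 2.1.2 excludes "Allogeneic stem cell transplant within 100 days", so later allograft recipients can enroll.
- Section 5.5.4 handles actionable germline findings thus: "Subjects will be contacted with a request to provide a blood sample to be sent to a CLIA certified laboratory".

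**The concern.** A matched normal works only if it is free of tumor. In CLL, blood is often tumor tissue, and the protocol treats it so elsewhere: the baseline FISH panel, which includes the ATM and TP53 loci, is run on peripheral blood (Section 2.4.2). If the same tissue serves as the normal, the clone's mutations appear on both sides of the comparison and the Section 5.3.5 rule removes them. The fully clonal mutations are the most exposed, because they have the highest fraction in the contaminated normal. Candidate biomarkers of response could be lost in a way that depends on leukemic burden, which may itself relate to response.

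Allograft recipients raise a separate problem. If their blood is largely donor-derived, it lacks recipient germline variants that the donor does not share. Those variants would then be absent from the normal and pass as somatic.

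There is also a possible consequence for patients. A clonal variant read as germline could go forward for confirmation under Section 5.5.4 on another blood sample containing the same clone.

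**Working it through.** The documents give no figure for this, so there is none to reproduce. The check asks how much of a clonal mutation would be seen in a blood normal.

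**Inputs from the documents:** the 5x10^9/L diagnostic count (Section 1.2.2); the 20% call threshold, the 25X minimum and the 30X and 100X target depths (Section 5.3.5).

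**Assumptions:** diploid locus; heterozygous mutation in every leukemic cell; no sequencing error; no cell separation; 0.75 to 8x10^9/L other nucleated cells. The low end equals the neutrophil floor for entry (750/mcL, Section 2.1.1); the high end is my choice. The matched normal in Section 5.3.5 is taken to be the germline sample, the only one described.

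**Formulas:** with L leukemic and O other cells, the leukemic share is f = L/(L+O) and the expected mutant fraction is v = f/2. It exceeds 20% when f exceeds 40%; at L = 5 this means O below 7.5. At 30X, more than 20% means at least 7 mutant reads, with probability P(Binomial(30, v) ≥ 7). The chance of at least one mutant read is 1 − (1 − v)^30.

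| L (x10^9/L) | O (x10^9/L) | f | v | P(>20% of reads), 30X | P(≥1 read), 30X |
|---|---|---|---|---|---|
| 0 | 5 | 0% | 0% | 0 | 0 |
| 0.1 | 5 | 2.0% | 1.0% | 0.00 | 0.26 |
| 1 | 5 | 16.7% | 8.3% | 0.01 | 0.93 |
| 5 | 8 | 38.5% | 19.2% | 0.35 | 0.998 |
| 5 | 4 | 55.6% | 27.8% | 0.77 | >0.999 |
| 5 | 0.75 | 87.0% | 43.5% | 0.99 | >0.999 |
| 20 | 8 | 71.4% | 35.7% | 0.95 | >0.999 |
| 20 | 0.75 | 96.4% | 48.2% | >0.99 | >0.999 |

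The last two columns are two readings of presence in the normal: called at the protocol's own threshold, or seen in any read. They diverge most at low burden. At L = 1 the chance of loss is 1% on the first reading and 93% on the second. At L = 20 or more it is at least 95% on both.

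A true heterozygous germline variant has an expected fraction of 50%. At L = 20 the contaminated normal shows 36% to 48%. A better comparison rule therefore cannot reliably rescue a blood normal at high burden, and the source has to change as well.

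For donor blood the logic is directional. A recipient tumor mutation is not in donor cells, so donor cells cannot cause it to be filtered out. A recipient germline variant that the donor lacks is in the tumor but not in donor cells, so it passes the filter as a false somatic call.

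**The case against.** The strongest reply is that the risk is conditional. Saliva is preferred, so blood may seldom be used. Eligibility does not require lymphocytosis: SLL is eligible, nodal or splenic disease alone can qualify as active, and Section 1.2.1 describes disease without blood involvement. The 5x10^9/L figure is a diagnostic criterion, not an on-study count, and a sample taken after obinutuzumab may hold few B cells. Section 5.3 also leaves methods open until samples are analyzed. Most of this stands, and it limits how often the loss would occur. The deferral, however, concerns analytic methods. It does not restrict the specimen, and a patient who leaves the study with only a blood normal may have no substitute.

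A reader might also infer four stronger things that the documents do not support:

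- *That mutations will be lost whenever blood is used.* The table runs from no loss to near-certain loss, and the 5x10^9/L case straddles 20%. The 20% figure is a calling threshold; nothing says it defines presence in the normal.
- *That donor-derived blood filters out somatic mutations.* The error runs the other way. Loss in these patients again needs leukemic cells in the sample. How far their blood is donor-derived is not stated.
- *That patients would look negative for TP53 or ATM lesions.* FISH at those loci and karyotype do not use the germline sample, and Section 5.3.5 describes Sanger sequencing of recurrently mutated genes separately from the matched-normal filter. Some of this information survives.
- *That blood testing under Section 5.5.4 would confirm a leukemic variant as heritable.* That needs several steps in sequence, and the confirming laboratory's method is not described. It is a possibility only.

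**Conclusion.** The point holds in conditional form. The plan allows unsorted blood as the normal and drops what is found there. Where blood is used and leukemic cells exceed about 40% of nucleated cells, the expected fraction of a clonal heterozygous mutation passes 20% and loss is likely. It is near-certain at 20x10^9/L or more across the assumed 0.75 to 8x10^9/L of other cells, uncertain around 5x10^9/L, and nil without circulating disease. At low counts the answer turns on an undefined term, presence in the normal. Subclonal mutations would have lower fractions than those tabulated.

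For allograft recipients beyond 100 days the risk is false somatic calls, whose size cannot be derived from the documents.

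The consequence is confined to exploratory genomic analyses in at most 24 patients, with a possible effect on incidental-finding confirmation. DLT, MTD and response do not depend on it. The change is worth making because it is cheap and a lost normal may not be recoverable.

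**What to change.** 1. In Sections 2.4.5, 5.1, 5.2.4.1 and 5.3.4, remove unsorted blood as a germline source and use the saliva or buccal kits already named.
2. If only blood exists, analyze the patient as tumor-only and flag this in every report.
3. In Section 5.3.5, replace absence from the matched normal with a stated comparison of allele fraction in tumor and normal. This also covers leukocytes carried in saliva or buccal samples, which the documents do not address.
4. State that blood is not used as the normal after an allogeneic transplant.
5. In Section 5.5.4, confirm on a non-blood sample when circulating CLL or a prior allograft is present.

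The cost is a wording amendment, an occasional repeat swab or saliva kit for low DNA yield, minor pipeline work for item 3, and arranging a non-blood specimen with the confirming laboratory for item 5. Cell sorting is not needed.
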